8.4. Imputation of Missing Data

8.4.1. Multiple Imputation of Missing Ordinal Clinical Response and DOOR at Outcome Assessment Visit #1 and Outcome Assessment Visit #2

Several analyses, including the primary analysis, depend on multiple imputation of DOOR or OCR at Outcome Assessment Visit #1 or Outcome Assessment Visit #2. Multiple imputations of each of these missing endpoints will be performed independently, and each subject will have their missing endpoints imputed independently of other subject’s imputations using a subject-specific imputation model.

As a first step to multiple imputation, an ordered list of variables to include in the subject-specific imputation model is constructed. Ordering is specified so that exact imputation results from final data are prespecified may be replicated in SAS (using seeds described below). The complete ordered list of variables for the imputation models for DOOR at Outcome Assessment Visit #1 and OCR at Outcome Assessment Visit #1 is below.

- Indicator of subject enrolled at the site with the second most number of subjects enrolled (binary indicator)
- Indicator of subject enrolled at the site with the third most number of subjects enrolled (binary indicator)

-
- Indicator of subject enrolled at the site with the least number of subjects enrolled (binary indicator)
 - Note: the site with the most number of subjects enrolled is reference for site. Language is written to allow for an arbitrary number of sites. In the event of a number of ties for the number of subjects enrolled, tied sites will be ordered in ascending alphanumeric order in the list of model variables.
 - Indicator of amoxicillin (not amoxicillin placebo) as study treatment (binary indicator)
 - Indicator of amoxicillin-clavulanate (not amoxicillin-clavulanate placebo) as study treatment (binary indicator)
 - Indicator of cefdinir (not cefdinir placebo) as study treatment (binary indicator)
 - Note: placebo is the reference group for study treatment
 - Indicator for amoxicillin-clavulanate as initial antibiotic (binary indicator)
 - Indicator for cefdinir as initial antibiotic (binary indicator)
 - Note: amoxicillin is the reference group for initial antibiotic
 - Indicator for age ≥ 2 years at enrollment (binary indicator)
 - Indicator for initial treatment site for pneumonia at an emergency department (binary indicator)
 - OCR at Outcome Assessment Visit #2 (imputed OCRs will not be used)
 - Severity of cough on Day 1 as recorded on Solicited Events form (0, 1, 2, or 3)
 - Note: amoxicillin is the reference group for initial antibiotic
 - Severity of most severe solicited event (besides cough) on Day 1 (0, 1, 2, or 3)
 - Note: Some missing values for Day 1 will first be imputed as described in Section [6.5.4](#)
 - Severity of cough on Day 2 as recorded on Solicited Events form (0, 1, 2, or 3)
 - Severity of most severe solicited event (besides cough) on Day 2 (0, 1, 2, or 3)
 - Note: Some missing values for Day 2 will first be imputed as described in Section [6.5.4](#)
 - Severity of cough on Day 3 as recorded on Solicited Events form (0, 1, 2, or 3)
 - Severity of most severe solicited event (besides cough) on Day 3 (0, 1, 2, or 3)
 - Note: Some missing values for Day 3 will be first imputed as described in Section [6.5.4](#)
 - Severity of cough on Day 4 as recorded on Solicited Events form (0, 1, 2, or 3)
 - Severity of most severe solicited event (besides cough) on Day 4 (0, 1, 2, or 3)
 - Note: Some missing values for Day 4 will first be imputed as described in Section [6.5.4](#)
-

- Severity of cough on Day 5 as recorded on Solicited Events form (0, 1, 2, or 3)
- Severity of most severe solicited event (besides cough) on Day 5 (0, 1, 2, or 3)
 - Note: Some missing values for Day 5 will first be imputed as described in Section 6.5.4

For DOOR and OCR at Outcome Assessment Visit #2, the complete list of model variables is identical to the above, but with OCR at Outcome Assessment Visit #2 replaced with OCR at Outcome Assessment Visit #1. Additionally, cough severity and most severe solicited event are listed up to Day 18 rather than Day 5.

The actual list of model variables for each subject-specific imputation model will follow the ordering above but omit variables with missing values. The below pseudo-code / SAS code outlines the creation of 20 multiple imputation datasets. Note that the seeds used in the actual analysis must follow the specification given in the pseudo-code and subjects must be processed in the order described in the pseudo-code. OCR will simultaneously be imputed with DOOR at each respective Outcome Assessment Visit. The pseudo-code is in terms of the Outcome Assessment Visit #1 endpoints, but the general logic is also applicable to the Outcome Assessment Visit #2 endpoints (with references to “V1” replaces with references to “V2”).

DEFINE i=index variable for subjects having DOOR imputed.

Subjects requiring imputation are sorted in ascending order
by PATID.

DEFINE N=number of subjects requiring imputation

DEFINE g&i=analysis dataset containing predictors and DOOR for
CC-V1 subjects as well as subject i (only one subject not in
CC-V1 included). Note that CC-V1 subjects that are missing a
value
for one or more variables in the subject-specific imputation
model are excluded.

DEFINE imp_g&i = g&i, with 20 imputed values for the missing DOOR
added by PROC MI

DEFINE &&modelVars_&i = list of observed variables in subject i, to
be used for imputation of DOOR and OCR.

%do i=1 %to &N;

```
PROC MI data=g&i out=imp_g&i seed=1200&i NIMPUTE=20 noprint;
  var &&modelVars_&i DOOR OCR;
  monotone reg(DOOR_V1 = &&modelVars_&i);
  monotone reg(OCR_V1 = &&modelVars_&i);
```

```
run;
```

```
%end;
```

```
imp_g&i will be subset to contain only rows for the subjects with  
imputed DOOR and merged together and with CC-V1 data to create the  
twenty complete multiply imputed datasets
```

```
*****
```

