7.5 Early Termination Visit

Subjects who are withdrawn from the study will be asked to complete an early termination visit. Procedures at the early termination visit will be identical to the outcome assessment visits except no throat swab or stool specimen (if consented to participate in the collection of future use samples) will be collected. Unless they expressly state that they wish to have no additional

follow-up or data collection, subjects who withdraw from the study will receive a follow-up phone call approximately one week after their withdrawal. Study staff will review the memory aid and determine if any follow-up medical care was sought.

If the subject presents with symptoms such as fever and/or elevated respiratory rate at the Early Termination visit, the study team will inform the subject's PCP/pediatrician and will urge the parent(s) to follow-up with their primary provider.

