11.4.1 Primary Analysis

For the primary analyses, the DOORs will be compared between the 5- and 10-day arms. The sum of the probability that a randomly selected subject will have a better DOOR if assigned to the 5-day arm for Outcome Assessment Visit #1 plus one-half the probability of equal DOORs for Outcome Assessment Visit #1 will be estimated. The null hypothesis to be tested is that the probability is equal to 0.50 (lack of superiority of short-course therapy). The primary analysis will be carried out using the ITT cohort, with missing DOOR values (treated as continuous)

imputed using multiple imputation, utilizing linear regression models corresponding to relevant observed data (baseline covariates and observed DOOR components from an early termination visit, if available). The Mann-Whitney U statistic will be combined across the datasets to give the test statistic and Rubin's Rules used to define distribution of the test statistic under the null hypothesis. The test of the null hypothesis will be two-sided with a Type I error of 0.05. A point estimate of the estimand will be computed by dividing combined test statistic by the number of pairwise comparisons and a confidence interval of the estimand will be computed by inverting the described test of the null hypothesis.

Note: Subjects will be asked to confirm fever with repeat testing after approximately 15 minutes; for analysis purposes, subjects lacking a repeat measurement will be considered as having developed fever.

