6.5. Missing Data

While all efforts will be made to minimize missing data, some missing data is expected. Whenever possible, subjects terminating from the study early will be given an early termination visit during which the available components of the DOOR and related measures can be recorded. The primary analysis will use multiple imputation with linear models to impute values using available information (treatment, randomization strata variables, and available visit information), assuming a missing at random (MAR) model. Secondary analyses will further examine the robustness of this analysis, including a “worst case analysis” in which all imputations of missing

data will be the worst case (result in the lowest possible DOOR given available information) for subjects in the 5-day arm and best case for subjects in the 10-day arm. Day 1 in this study is defined as the date of first receipt of study product. If a subject has no record of study product administration or did not receive a first dose of study product, but has other post-randomization data, Day 1 will be imputed as the date 5 days after the date of first receipt of initial antibiotic.

In some cases, a subject may have DOOR defined despite missing some of its components, in which case the subject will be eligible for inclusion into the CC and ATP analysis populations. In analyses of the components of the DOOR using the CC and ATP analysis populations, data will be analyzed as available and missing data will not be imputed.

The study includes several composite variables with rules for assignment, missingness, and imputation described below.

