6.5.1. Adequate Clinical Response to OAV#1 or OAV#2

Subjects that have no record of receipt of at least one dose of study product will have adequate clinical response and its components considered missing at both OAV#1 and OAV#2. Otherwise, if a subject dies at any point during subject participation in the study, the subject will be considered as not having adequate clinical response at OAV#1 or OAV#2. Otherwise, if a subject does not have OAV#1 then ACR and its components are missing for OAV#1 and if a subject does not have OAV#2 then ACR and its components are missing for OAV#2.

Several variables are used to define the Adequate Clinical Response:

- MAVABRX: Was the subject prescribed or did the subject receive an additional antibiotic treatment at this visit? (Yes/No)
 - o MAVABCP: If Yes, was the antibiotic given for pneumonia or treatment for a complication of pneumonia? (Yes/No)
- MAVPLEUR: Drainage of pleural fluid as treatment for pneumonia or a complication of pneumonia? (Yes/No)
- MAVCHTB: Placement of a chest tube as treatment for pneumonia or a complication of pneumonia? (Yes/No)
- MAVVIDEO: Video assisted thoracoscopic surgery as treatment for pneumonia or a complication of pneumonia? (Yes/No)
- MAVTHOR: Thoracotomy procedure as treatment for pneumonia or a complication of pneumonia? (Yes/No)
- MAVSURG: Any other surgical procedure as treatment for pneumonia or a complication of pneumonia? (Yes/No)
- MAVHOSP: Was the subject hospitalized at this visit? (Yes/No)
 - o MAVHPPN: If Yes, was the hospitalization for the treatment of pneumonia or pneumonia complications? (Yes/No)

If a subject has OAV#1 and did not have a medically attended visit (MAV) from Day 1 to Day 5, inclusive, then the subject had adequate clinical response for OAV#1. If the subject had a MAV from Day 1 to Day 5 for which MAVABRX and MAVABCP were both YES (receipt of a non-

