13. SUMMARY OF CHANGES IN THE CONDUCT OF THE STUDY OR PLANNED ANALYSES

Changes in the Conduct of the Study

Enrollment into the study was initiated under protocol version 2.0. Substantive changes to the protocol after study initiation are provided below.

Substantive changes in protocol version 3.0

- Removed 200mg/5mL amoxicillin and 200mg/5mL amoxicillin-clavulanate as possible dose strengths under Protocol Section 6.1.2. No subjects were prescribed under this dose.
- Clarified timing of interim analysis to be after at least 30% of the targeted subjects have completed the study instead of approximately 30%.

Changes to the Planned Analyses

There are no changes to the planned analyses as described in the protocol.

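### The SAP's closed imputation list omits the early termination visit outcomes that the protocol says will inform the primary endpoint, and its visit rule turns documented early failures into missing data

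*SAP*

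**What the plan says.** **Protocol.** Section 7.5: "Procedures at the early termination visit will be identical to the outcome assessment visits except no throat swab or stool specimen". Appendix A marks vital signs, medical history, concomitant medications, record review, memory aid review, clinical response and solicited events at that visit. Section 11.4.1 names the inputs to imputation of the primary endpoint as "baseline covariates and observed DOOR components from an early termination visit, if available".

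**SAP, general text.** Section 6.5 describes an "early termination visit during which the available components of the DOOR and related measures can be recorded" and says imputation will use "treatment, randomization strata variables, and available visit information".

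**SAP, operative text.** Section 8.4.1 presents "The complete ordered list of variables for the imputation models for DOOR at Outcome Assessment Visit #1". The list holds site, study treatment, initial antibiotic, age group, emergency department as initial treatment site, ordinal clinical response (OCR) at OAV#2, and diary grades of cough and worst solicited event for Days 1 to 5. Subject-specific models may drop an item that is missing. Nothing allows an item to be added, and the order and seeds are fixed so that results can be replicated.

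**SAP, missing-data rules.** Section 6.5.1: "if a subject does not have OAV#1 then ACR and its components are missing for OAV#1". Death is the exception. Section 6.5.6 likewise makes antibiotic days missing for a child with no outcome visit, except after death or hospitalization for pneumonia. Section 6.3 excludes early terminators before OAV#1 from the CC-V1 cohort.

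**SAP 13.** "There are no changes to the planned analyses as described in the protocol".

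**The concern.** The primary analysis assumes missing at random given the predictors in the model. Families may leave because the child is relapsing or has side effects, and the ETV is where that would be measured. If the ETV findings do not enter the model, a child seen to be febrile or tachypneic is imputed as if only the diary were known. If a failure was already documented, it is replaced by a draw from a model fitted to completers. Either makes missing at random harder to defend, in the analysis that carries the trial's conclusion. The SAP also departs from the protocol's stated primary method while saying that it does not.

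**Working it through.** **1. Components side by side.**

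| DOOR component | Available at the ETV (Protocol 7.5, Appendix A) | In the SAP 8.4.1 list for OAV#1 |
|---|---|---|
| Fever | Yes | No |
| Respiratory rate | Yes | No |
| Cough | Yes, graded at the visit | Diary grade only, Days 1-5 |
| Solicited events | Yes | Yes, daily worst grade from the diary |
| Adequate clinical response (ACR) | Yes | No |
| Antibiotic days | Yes, from memory aid and medications | No (study treatment is included) |

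Fever and respiratory rate are two of the three criteria that separate OCR 1-4 from OCR 5. Neither is in the model in any form.

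**2. Two children traced through the rules.**

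- *Child A* leaves on Day 8 with a full ETV. There is no OAV#1 on record, so ACR is missing (6.5.1), OCR is missing (6.5.5), DOOR is missing (6.5.7), and the child is outside CC-V1 (6.3). No rule accepts the ETV as the visit, although it falls in the Day 6-10 window with the same assessments.
- *Child B* has a medically attended visit on Day 3 with a non-study antibiotic for pneumonia, then leaves. The 6.5.1 pseudocode asks whether OAV#1 took place before it looks at medically attended visits, so ACR is missing. OCR should be 6 by definition but is missing, and the failure is not a predictor. Had Child B been hospitalized for pneumonia, 6.5.6 would supply antibiotic days, but OCR would still be missing.

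**3. Number of children.** SAP 5 (Noether): N = (1.960 + 1.282)² / [12 × 0.5 × 0.5 × (0.60 − 0.50)²] = 350.2. The plan uses 360, and 360 / 0.90 = 400. Planned losses are 400 − 360 = 40, about 20 per arm. The documents do not say how many of these would have an ETV.

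**4. Size for the primary DOOR (assumed inputs).** Suppose *m* of 200 short-course children leave early with an ETV, a share *s* are symptomatic or failing, their true probability of a better DOOR is *f*, imputation places them at 0.60, and the standard course has no such children. The overstatement is m × s × (0.60 − f) / 200.

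- Low: 5 × 0.25 × (0.60 − 0.10) / 200 = 0.003
- Middle: 10 × 0.50 × (0.60 − 0.10) / 200 = 0.0125
- High: 20 × 1.00 × (0.60 − 0) / 200 = 0.06

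**5. Size under one assumed OCR distribution.** Take 45/25/10/3/12/4/1/0% for levels 1 to 8 in both arms, with 5 or 10 of 200 short-course early terminators truly at OCR 5 and none in the standard course.

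- *OCR (secondary).* An OCR 5 child scores 0.05 + 0.12/2 = 0.11 against an average of 0.50. The shift is 5/200 × 0.39 = 0.010, or 10/200 × 0.39 = 0.020. The distance from 0.50 to the non-inferiority limit of 0.40 is 0.10.
- *DOOR (primary), 0 versus 5 antibiotic days.* P(equal OCR) = 0.292, so the probability is (1 − 0.292)/2 + 0.292 = 0.646. An OCR 5 short-course child scores 0.05 + 0.12 = 0.17. The shift is 5/200 × 0.476 = 0.012, or 10/200 × 0.476 = 0.024, giving 0.634 or 0.622.
- *Standard error at 200 per arm, ignoring ties.* √[401 / (12 × 200 × 200)] = 0.029. Both shifts are below it.

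**The case against.** A reader might infer that the SAP never uses the ETV, that measured symptoms of early terminators are thrown away, and that an imbalance between arms would be hidden. The documents do not support any of these.

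- SAP 6.5 names the ETV and speaks of available visit information. Diary cough and solicited events up to termination stay in the model.
- ETV cough and fever are listed by arm (Listings 15-18). Terminations before OAV#1 are tabulated by reason and arm (Table 5).
- The worst-case ITT analysis (SAP 8.2.2.5) sets missing short-course OCR to 8, or to the larger of 5 and the OAV#2 value where that exists, and treats missing standard-course data as benign. That is harsher on the short course than any scenario above.
- Stopping study product is not study withdrawal (Protocol 9.5.2), and children with an inadequate response are asked to complete both visits (Protocol 4). An ETV applies only when a family declines the remaining visits. A family attending on Day 6-10 could simply complete Visit 2.
- The size calculations are one-sided and give the diary predictors no credit.

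All of this stands, and it limits the likely effect. It does not reconcile SAP 8.4.1 with Protocol 11.4.1, because a list declared complete overrides a general phrase in 6.5. The worst-case analysis is a bound in one direction that ignores what the ETV showed. It does not replace using the data in the primary analysis. Nor does anything above rescue Child B's documented failure.

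**Conclusion.** The point holds as a conflict between documents with a probably small numerical effect. SAP 8.4.1 omits ETV components that Protocol 11.4.1 says will inform the primary imputation. SAP 6.5.1 and 6.5.6 leave no other route in, so in-window ETVs go unused and a pneumonia failure documented before termination becomes missing. The statement in SAP 13 is wrong on this point. The loss of documented failures is arguably the more consequential part, since OCR 6 or 7 ranks below persistent symptoms.

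The illustrated shift in the DOOR probability is 0.003 to 0.06 against a design effect of 0.10. The top of the range needs all 20 planned short-course losses to have an ETV and be failing, with none in the other arm. In the worked distribution the primary result stays well above 0.50. These figures rest on assumed numbers of ETVs, an assumed OCR distribution and a fully one-sided imbalance. An imbalance the other way would reverse the sign. Sample size, alpha and planned power are unaffected.

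It would also go too far to say that the protocol promises to count an ETV as an outcome visit. Section 11.4.1 promises only that ETV components inform imputation. Accepting in-window ETVs is a recommended improvement.

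**What to change.** 1. In SAP 3.3, 6.3 and 6.5.1 to 6.5.6, accept a complete ETV held on Day 6-10 as OAV#1 and one held on Day 19-25 as OAV#2. The procedures are the same, so no imputation is needed for these children.
2. In SAP 6.5.1 and 6.5.5, test for a documented qualifying medically attended visit or pneumonia hospitalization in the window before testing whether the outcome visit took place. An observed failure then gives ACR = NO and OCR 6 or 7. Section 6.5.6 needs a matching rule for antibiotic days, because 6.5.7 leaves DOOR missing if days are missing and the present exception covers only death and pneumonia hospitalization.
3. For ETVs outside the windows, reconcile 8.4.1 with Protocol 11.4.1 in one of two ways. Either add ETV items with a stated mapping, for example as a sensitivity analysis, or declare and justify the departure in SAP 13. The mapping must not equate an early ETV symptom with the same symptom at the outcome visit. In completers, those visit symptoms define OCR 5 (6.5.3, 6.5.5), so the fitted relation is near-deterministic. Enrollment permits grade 2 cough, so a Day 2 ETV with grade 2 cough would be pushed toward persistent symptoms at Day 6-10.

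**Cost.** SAP wording and a few programming lines, with no new data. Any mapping of an ETV held before Day 6 remains an approximation.

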5. SAMPLE SIZE CONSIDERATIONS

The null hypothesis corresponding to the primary analysis of this study is:

H0: The sum of the probability that a subject assigned to the 5-day arm will have a higher DOOR than if assigned to the 10-day arm plus one-half the probability of equal DOORs is 50% (i.e., no difference in DOOR).

The primary study sample size is based on a superiority test of the null hypothesis above, under an assumed alternative hypothesis that the sum of the probability that a subject assigned to the 5-day arm will have a higher DOOR than if assigned to the 10-day arm plus one-half the probability of equal DOORs is 60% (p=60%).

A sample size of 360 (180 per arm) provides 90% power using a 2-sided alpha=0.05 with a Wilcoxon Mann-Whitney U test (see calculation below). If p=65% or 70%, then a total sample size of 160 (80 per arm) or 90 (45 per arm), respectively, would be required. The sample size is inflated by ~10% based on an estimate from a similar study, in order to account for loss to follow-up resulting in a total sample size of 400 (200/arm).

Sample size calculations were based on the formula below (Noether 1987):

$$N = \frac{(z_{\alpha} + z_{\beta})^2}{12c(1-c)\left(p'' - \frac{1}{2}\right)^2}$$

$$z_{\alpha} = \Phi^{-1}(0.975); z_{\beta} = \Phi^{-1}(0.90); (90\% \text{ power for two-sided test with } 5\% \text{ Type I error})$$

$$c = 0.5 \text{ (equal allocation to treatment arms)}$$

$$p'' = 0.6 \text{ (Pr(Higher DOOR) under alternative hypothesis)}$$

Note that the primary analysis statistical methods use the ITT analysis population and will account for missing data with multiple imputation. The exact analysis method was not used for the power calculation because it would require an excessive amount of assumptions about the nature and patterns of missing data in the final dataset and relationships of components of the imputation model to the primary outcome. Instead, a complete case analysis assuming 90% evaluable for analysis was used to obtain approximately 90% power in the actual analysis.

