- Not excluded for any reason above, subject did not receive at least one dose of study product each day from Day 1 to Day 5
- Not excluded for any reason above, major protocol deviation (see Section 6.3.3; subjects will be tabulated by type of protocol deviation)
- Outcome Assessment Visit #1 occurred out of the protocol defined window of Day 6-10
- Outcome Assessment Visit #1 did not occur as an in-person visit

ATP-V2 Exclusion Reasons

- The subject was excluded from CC-V2 cohort
- Not excluded for any reason above, subject did not receive at least one dose of study product each day from Day 1 to Day 5
- Not excluded for any reason above, major protocol deviation (see Section 6.3.3, subjects will be tabulated by type of protocol deviation)
- Outcome Assessment Visit #2 occurred out of the protocol defined window of Day 19-25
- Outcome Assessment Visit #2 did not occur as an in-person visit

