6.5.3. Resolution of Symptoms at OAV#1 or OAV#2

Resolution of symptoms is defined as the absence of all of the following:

- Fever at the OAV, as defined above
- Elevated respiratory rate (RR >50 breaths/minute for children <24 months of age and >40 breaths/minute for children 24-71 months of age) at the time of the Outcome Assessment Visit (VS1.RESPB);
- Presence of cough grade 2 or 3 at the Outcome Assessment Visit (ACRCGHSV)

If the subject died at any point of participation in the study, then the subject will be analyzed as not having resolution of symptoms at either Outcome Assessment Visit. Otherwise, if the subject did not have adequate clinical response at OAV#1 or OAV#2, then the subject will be analyzed as not having resolution of symptoms at the respective Outcome Assessment Visit(s). Otherwise, if fever, elevated respiratory rate, or presence of grade 2 or 3 cough is indicated at OAV#1 or OAV#2, then the subject does not have resolution of symptoms at the respective Outcome Assessment Visit (regardless of whether some components of the resolution of symptoms are missing). Otherwise, if fever, respiratory rate, and presence of cough are all non-missing and are indicated as 'No' at OAV#1 or OAV#2, then the subject has resolution of symptoms at the respective Outcome Assessment Visit. Otherwise, resolution of symptoms is missing at the Outcome Assessment Visit.

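### The imputation list for DOOR omits the OAV#1 findings that decide which attending children with incomplete records have a missing outcome

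*SAP*

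**What the plan says.** SAP 6.5 says that the primary analysis imputes from "available information (treatment, randomization strata variables, and available visit information), assuming a missing at random (MAR) model". SAP 8.4.1 then fixes the predictors for the OAV#1 endpoints, introducing them as "The complete ordered list of variables for the imputation models for DOOR at Outcome Assessment Visit #1" and the matching OCR: site, study treatment, initial antibiotic, age group, emergency-department treatment, OCR at OAV#2, and diary cough and worst solicited event for each of Days 1 to 5. Predictors that a child lacks are dropped from that child's model. Donors are the complete cases (CC-V1). Adequate clinical response (ACR), fever, cough grade and respiratory rate at OAV#1 are not listed, and neither are antibiotic days.

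The rules for a child who was seen are these:

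- A recorded failure gives OCR 6 or 7 before symptoms or diary are consulted (6.5.5).
- One recorded symptom means that symptoms are not resolved, "regardless of whether some components of the resolution of symptoms are missing" (6.5.3), which gives OCR 5.
- With no symptom recorded and a component blank, 6.5.3 says: "Otherwise, resolution of symptoms is missing at the Outcome Assessment Visit". OCR and DOOR are then missing (6.5.5, 6.5.7).
- Two consecutive blank diary days, or more than two blank days, make event severity missing unless a grade 3 event is recorded (6.5.4). Severity matters only for children not already placed at OCR 5 to 8.

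Incomplete visits are foreseen. SAP 6.3 lists "Outcome Assessment Visit #1 did not occur as an in-person visit" as a reason for exclusion from ATP-V1, and respiratory rate could be unmeasured at such a visit.

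**The concern.** The same blank field removes a well child from the complete cases but leaves a coughing child in. The variables that separate the two are on record at the visit, yet the imputation model does not use them. It learns from donors who include all the OCR 5 to 7 children and applies that to children whose own records rule out those values or make them unlikely.

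This enters the primary ITT comparison. It also enters the ITT analyses of OCR, including the non-inferiority test against 0.40, because they use the same list, and the OAV#2 endpoints, whose list is built the same way. The error works against whichever arm has more such children.

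**Working it through.** **1. The plan's own figure.** Protocol 11.4.1: "The test of the null hypothesis will be two-sided with a Type I error of 0.05". SAP 5: "A sample size of 360 (180 per arm) provides 90% power using a 2-sided alpha=0.05 with a Wilcoxon Mann-Whitney U test". The Noether formula with c = 0.5 and p'' = 0.60 gives N = (1.960 + 1.282)² / (12 × 0.25 × 0.10²) = 350.2, so 351 against a stated 360. For p'' = 0.65 and 0.70 it gives 156 and 88 (stated 160 and 90). Power at 360 is 90.8%, and 360 / 0.9 = 400. The sample size reproduces and this point does not affect it. The design effect is 0.60 - 0.50 = 0.10.

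**2. Rules side by side**, for a treated child seen at OAV#1 with antibiotic days known:

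| What is blank | Symptom or failure recorded | None recorded |
|---|---|---|
| Respiratory rate | OCR 5 to 7, DOOR defined | OCR and DOOR missing |
| Two consecutive, or more than two, diary days | OCR 5 to 7, DOOR defined | OCR and DOOR missing, unless a grade 3 event is recorded |

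**3. Enumeration.** Listing every combination of component states under SAP 6.5.1 to 6.5.7 gives 576 with missing DOOR. Of these, 420 carry a recorded symptom or failure: 190 through missing ACR, 230 through missing antibiotic days, and 0 by any other route. A fever of unknown relatedness was coded as missing. These are counts of states, not frequencies.

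**4. Simulation of the 8.4.1 regression.** Assumptions, none of them from the documents except 400 children and 20 imputations: no OCR difference between arms; 0 against 5 antibiotic days; diary and visit cough correlated; OAV#2 OCR in the model; respiratory rate unmeasured in 5% or 10%; 150 trials per setting. Monte Carlo error was not computed. Rank 1 is best. Gap closed = (donor - imputed) / (donor - true).

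| OCR ≥5 | Unmeasured | True mean rank of missing children | Imputed, SAP list | Donor mean | Imputed, OAV#1 indicator added | Gap closed by SAP list | Bias, SAP list | Bias, indicator added |
|---|---|---|---|---|---|---|---|---|
| 7% | 5% | 178.1 | 188.7 | 191.0 | 178.3 | 18% | -0.0009 | +0.0001 |
| 12% | 5% | 171.9 | 187.6 | 191.4 | 171.2 | 20% | -0.0013 | -0.0001 |
| 21% | 5% | 150.9 | 179.5 | 192.7 | 151.3 | 32% | -0.0015 | +0.0001 |
| 7% | 10% | 168.9 | 179.3 | 181.4 | 169.0 | 16% | -0.0028 | -0.0009 |
| 12% | 10% | 158.9 | 176.4 | 182.8 | 159.7 | 27% | -0.0039 | -0.0008 |
| 21% | 10% | 145.9 | 173.3 | 184.1 | 144.8 | 28% | -0.0028 | +0.0003 |

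About 1% of the children with missing DOOR truly had OCR ≥5, against 7.5 to 22% of donors. With 15% unmeasured in the short-course arm and 5% in the standard arm, the bias was 0.6471 - 0.6537 = -0.0066 (12% OCR ≥5) and 0.6290 - 0.6394 = -0.0104 (21%). With the indicator added it was +0.0008 and -0.0001.

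**5. Two further simulations under other assumptions.**

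- 250 trials per setting, about 14% OCR ≥5, respiratory-rate or diary gaps, OAV#2 OCR left out. The bias was about -0.003 with 10% gaps in each arm, and -0.008 to -0.012 at 15% against 5% or 20% against 10%. For OCR under the same imbalance it was -0.010 to -0.012. Adding OAV#1 cough, fever and ACR cut the bias to at most 0.002 in absolute size.
- 300 trials, about 12% OCR ≥5, OAV#2 OCR included. The bias was -0.0008 at 3% gaps, -0.0023 at 10%, and -0.005 at 15% against 5%. Including OAV#2 OCR shrank it by only about a tenth.

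**6. Scale.** Ignoring ties, the null standard error with 200 per arm is √(401 / (12 × 200 × 200)) = 0.029. Balanced bias is 0.001 / 0.029 to 0.004 / 0.029, or about 0.03 to 0.14 SE. With the 10-point imbalance it is 0.005 / 0.029 to 0.012 / 0.029, or about 0.2 to 0.4 SE.

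**The case against.** Several stronger readings are tempting, and the documents do not support them.

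- **That MAR itself fails.** Missingness here depends on recorded ACR, fever and cough, so MAR given all observed data may hold. The fault is a model that leaves those data out, which is why adding them works.
- **That symptom-free children are imputed as average.** Day 1 to 5 solicited events are themselves an OAV#1 DOOR component. OAV#2 OCR carries some information on OAV#1 failure because its window starts at Day 1. In the balanced settings above, the list closes 16 to 32% of the gap.
- **That DOOR is missing only when nothing is recorded.** DOOR can be missing despite a recorded symptom if antibiotic days are missing (6.5.6) or medically-attended-visit fields are blank (6.5.1). A recorded fever of unanswered relatedness counts as missing (6.5.2). How often these occur is not stated.
- **That all missing outcomes are affected.** Children with no OAV#1 have no visit findings to add. The plan's roughly 10% allowance is for loss to follow-up, not for gaps among attenders.

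It is also fair to say that vital signs are a procedure at every visit, diaries are reviewed with parents, one or two non-consecutive blank diary days are filled by rule, and blinding gives no particular reason to expect a 10-point imbalance. All this stands and limits the size.

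The planned sensitivity analyses do not repair the fault. The complete-case analysis drops the same well children. The worst-case analysis gives short-course children OCR 8, or at least 5 if OAV#2 is known, even where their own OAV#1 record argues otherwise. It guards against error favouring short course but does not correct the primary estimate.

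**Conclusion.** The point holds for treated children seen at OAV#1 with an incomplete record. Their missingness depends on observed OAV#1 findings that the 8.4.1 list omits, contrary to what 6.5 promises, so the imputation is not MAR given the listed variables. These mostly symptom-free children are imputed too badly.

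The bias in Pr(higher DOOR) plus half of ties is about -0.001 to -0.004 with balanced gaps of 5 to 10%. It is about -0.005 to -0.012 with 10 points more gaps in the short-course arm, so at most about an eighth of the 0.10 design effect (0.012 / 0.10 = 0.12). An excess in the standard arm should push the other way by the same mechanism, but was not simulated. Gap rates, symptom prevalence and correlations are all assumptions. A reader might infer that the primary conclusion is in doubt, but these sizes do not support that. Priority is low to moderate: the bias is small, systematic and easily removed.

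**What to change.** Add to the 8.4.1 list, where observed, ACR, fever, grade 2 or 3 cough and elevated respiratory rate at OAV#1, with the OAV#2 equivalents for the OAV#2 endpoints. Where only antibiotic days are missing, use the child's known OCR as a predictor of DOOR; the present code regresses DOOR on the listed variables alone.

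Restricting imputed values to those compatible with the record is optional. If it is done, it must be defined for DOOR as well as OCR, because DOOR is drawn from its own regression and truncated normal draws have effects of their own. One way is to impute the missing component and then derive OCR and DOOR from it.

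The cost is a few SAP lines, some code and slightly larger imputation models. The variables are already collected. Nothing changes for children without an OAV#1.
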